Family-centred care (FCC) is, in fact, developmentally supportive care that helps develop bonding (12). Intermittent kangaroo mother, as a part of FCC, benefits from maternal-neonatal bonding (13). Similarly, the role of maternal involvement in pre-feeding sensorimotor stimulation is a hidden corner in research. To our knowledge, not even a single international or national study is available in this regard.

In resource-constrained setups with limited properly trained speech therapists and neonatal nurses, mothers can be involved in pre-feeding sensory motor stimulation after training and teaching to improve their feeding performance. Within this context, the current study aims to determine the following: 1) the maternal role in sensory-motor stimulation for oral feed establishment in preterm neonates, 2) determine the effect of sensory-motor stimulation offered by the mother on the onset of oral feeding, and 3) the efficiency of mother-mediated stimulation techniques on oral feeding compared to trained nurses.

Keywords

Prematurity sensory-motor stimulation oral feed establishment, feeding intervention

Material and methods

An interventional, prospective, randomized control trial was conducted after ethical approval from the Institutional Review Board of Fatima Memorial Hospital (FMH-07-2021-IRB-929-M). The authors confirm that this intervention's ongoing and related trials are registered in the ClinicalTrials.gov platform—accession number NCT05484726. The study protocol can be accessed at <https://www.clinicaltrials.gov/ct2/show/NCT05484726>.

Study hypothesised that preterm babies who receive sensory motor stimulation from their mothers as compared to trained nurses, are

- Start taking oral feed at the same time as compared to the control group
- Take the same amount of milk at the commencement of oral feeding
- Take milk with equal efficiency
- Not face more adverse effects

The study period spans 16 months, from March 2022 to July 2023, in the department of Neonatology, Fatima Memorial Hospital, Lahore. We enrolled all preterm neonates of gestation age 28 to 34 weeks who were admitted to NICU during the study period after seeking consent from parents or guardians. All these neonates were haemodynamically stable, established gavage feed, had no respiratory distress, no need for respiratory support except LFNC and did not receive any kind of analgesics at time of enrollment.

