However, all those neonates having major anomalies incompatible with life, major malformations, syndromic babies, cleft lip and palate, genetic disorders, haemodynamically unstable babies including IVH (grade III & IV), haemodynamically significant PDA (HsPDA) requiring antifailure therapy, NEC (stage II & III) or anemia requiring blood transfusion. All those neonates with adverse events including cough with choking, breath holding, choking, aspiration, tachycardia HR > 200/min, bradycardia HR < 100/min, apnea > 15 sec, tachypnea RR > 70/min while stimulation or feeding were excluded.

Protocol

Interventional Study Model: Factorial Assignment

- Maternal involvement in perioral sensory-motor stimulation be in three stages
 - Observer status
 - Performing under supervision
 - Independent
- Intervention period: 5 days as
 - Training phase (T): T1 and T2 (for mothers by the nurse)
 - Direct feeding phase (D): F1, 2, and 3 (oral feed was offered to neonate)
- Stimulation for 7 minutes and 15 minutes before feeding twice a day at 1100 and 1700 hrs.
- Two groups
 - Intervention group (G I): by mothers
 - Control group (G II): by staff nurses

Number of Arms: 2

Masking: Single (Care Provider)

The mothers, medical staff involved in general care, nursing staff involved in the intervention, and doctors conducting the assessment of oral feeding skills (OFS) were all blinded to allocation. The nursing staff was informed at the time of intervention that participating infants received either sensory motor stimulation or sham oral stimulation depending on group allocation.

Allocation

Randomization was done using a random Alloc Software environment. Gestation age-based stratification was done using 3 blocks design of 28 to 30, 30+1 to 32 & 32+1 to 34. Random allocation of neonates into the intervention or control groups by stratum using lottery method.

Blinding

The mothers, medical staff involved in general care, nursing staff involved in intervention and doctors conducting the assessment of oral feeding skills (OFS) were all blinded to allocation. The nursing staff was informed at the time of intervention that participating infants received either sensory motor stimulation or sham oral stimulation depending on group allocation.

Sample size

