The sample size was 46 (23 each in interventional and control groups) and calculated with a 95% confidence level, 10% margin of error and 5% level of significance by taking feeding-related problems as 40%. It was done by using openepi.com.

Initially only 46 neonates were enrolled in study. But later an immense maternal response was observed. Mothers were ready to learn and involve in sensory motor stimulation of their neonates. Hence, the final total study population size was 97 with 49 in experimental and 48 in control group.

Procedure of intervention

- The study intermediation was started not before 30 weeks of postmenstrual age when full gavage feeding was established with the addition of supplements.
- All mothers in this study was involved in gavage feeding before involvement in the procedure.
- Trained nurses taught details of sensory-motor stimulation to mothers in easily understandable languages (annexure 1 in (a) English and (b) Urdu). This procedure has been adapted from modified from PIOMI and Fucile (14,15).
- Stimulation was done for 7 minutes and at least 15 minutes before feeding twice daily at 1100 and 1700 hrs till full oral feed establishment (expected time 28 days chronological age)
- Oral feeding was offered using a bottle with a slow-flow nipple.
- Time monitoring for feeding was strictly followed
- Infants was fed for a maximum of 20 min, and feeding was discontinued early if adverse events occur.

Arms and intervention

- Study groups for sensory motor stimulation (5 minutes) + pacifier (2 minutes)
 - Intervention group (G1) : by mothers
 - Control group (G 2) : by staff nurses

Experimental: Intervention group (Group 1)

- Maternal involvement was done in three stages for the intervention group as
 - Observer status
 - T1: Nurses performing all steps while mother observer status
 - T2: Nurses perform all steps in front of the mother and a pacifier was offered by the mother
 - Performing under supervision
 - D1: Mother performs all steps and oral milk was offered by the nurse while the mother observes.
 - D2: Mother performing all steps and offering oral milk while the nurse is supervising

- Independent
 - D3: Mother performing all steps independently
- Study groups for sensory motor stimulation
 - Assigned intervention perioral sensory motor stimulation Step 1 - 6 over 5 minutes + pacifier 2 minutes for total duration of 7 minutes.

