 - Step 1: With the help of the index finger, on the external surface of the cheek, make a circle starting from the angle of the mouth towards the ear then back 7x each cheek
 - Step 2: While holding both sides of the cheek with help of the thumb and index finger repeat step 1 7x each cheek
 - Step 3: Move index finger from one corner to opposite one over both lips separately 7x each lip
 - Step 4: Gentle massage and compress the gums from center to back of mouth 7x each half of the gum
 - Step 5: Move the finger from front to back on the hard palate while applying gentle pressure 7x
 - Step 6: Displace the center of the tongue with gentle pressure 7x
 - Offer pacifier at the end 2 minutes Note: 7x means 7 times

Control group / Sham Comparator (Group II)

All steps were same as intervention group and was performed by trained staff nurses

Data Collection

All relevant maternal and neonatal data (baseline measures) were collected on a specially designed proforma.

Baseline measures

- Maternal demographic and clinical data include
 - Age in years
 - Gravidity / number of pregnancies measured in numbers as primigravida (PG), 2-3 or ≥ 4)
 - Educational qualification as uneducated, primary, secondary or higher
 - Previous preterm baby measured as yes or no
 - Job status as working-lady or home-maker
 - Diabetes mellitus, hypertensive disorders and anemia as yes or no
- Neonatal demographic data includes
 - Gender as male or female
 - Gestation age measured in weeks
 - Mode of delivery as spontaneous vaginal delivery (SVD) or low segment caesarian section (LSCS)
 - Birth weight measured in kg
 - Weight for gestation age. It can be appropriate for gestation age (AGA), small for gestation age (SGA) or large for gestation age (LGA)
 - Place of birth as inborn or out-born
 - Neonates with respiratory failure may need respiratory support that was measured as
 - Requirement of invasive mechanical ventilation (IMV) along with duration in days as median with IQR

- Non invasive ventilation (NIV) along with duration in days as median with IQR
- Oxygen as low flow nasal cannula (LFNC) along with duration in days as median with IQR
- Neonates with prophylactic caffeine therapy given to all neonates < 32 weeks of gestation age
- Respiratory distress syndrome (RDS) was diagnosed on clinical and radiological features of reticulo-nodular shadowing
- Apnea was diagnosed on basis of breath holding spells for > 20 second

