- Hemodynamically significant patent ductus arteriosus (HsPDA) diagnosed by echocardiography
- Necrotizing enterocolitis (NEC) diagnosed using modified Bell's scoring (stage 1)
- Feeding intolerance diagnosed as aspirates > 20% of previous feed ± abdominal distension of > 2cm from base line
- Sepsis (leukocytosis or leukopenia or ANC<150 along with raised CRP and platelets <100 and or positive blood culture)
- Seizures
- Discharge weight in kg
- Duration of stay in NICU in days
- Neonatal feeding characteristics at time of enrollment in study include
 - Postmenstrual age (PMA) measured in weeks
 - Chronological age (ChA) measured in weeks
 - Time/duration to achieve full gavage/tube feed measured in days
 - Daily milk intake (ml/kg/day) when sensory motor stimulation was started
 - Volume of feed prescribed for each feed (ml)

The **outcome** measured were documented daily twice a day (11.00 and 17.00 hrs) until achievement of full oral feed. Full oral feed was volume of 120-140ml/kg/day taken orally. However, to make calculations concise, for both groups, all outcome parameters were documented on proforma for fixed time (11.00 am) for D1, D2, D3, D5, D7 and D14.

- Primary Outcome Measure
 - Transition time to full oral feeding is the time interval between commencement of perioral sensory stimulation on D1 to establishment of full oral feed in both groups. It was done daily till 14th day of perioral sensory motor stimulation. Transition time to full oral feeding was the day at which baby was able to take oral feed of volume of 120-140ml/kg/day.
 - Improvement (change) in efficiency oral feed establishment in terms of amount and time. It was classified into four levels depending upon the level of maturity in ascending order as follows:
 - Level 1: PRO < 30% and RT < 1.5 ml/min
 - Level 2: PRO < 30% and RT ≥ 1.5 ml/min
 - Level 3: PRO ≥ 30% and RT < 1.5 ml/min
 - Level 4: PRO ≥ 30% and RT ≥ 1.5 ml/min

For our RCT, efficacy was measured as the achievement of L4 for the intervention group vs the control group.

- Adverse outcome monitoring was done for every neonate from first day of enrollment in study (D1) till establishment of full oral feed (by D14 expected). These include non-life threatening adverse events including cough, tachycardia HR 180-200/min, bradycardia HR120 - 100/min, , tachypnea RR 60 - 70/min while maintaining SpO2 of >90% at room air
- Secondary Outcome Measure:
 - Total volume (TV) taken during each feed

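### D1, the origin of the primary outcome, is described in three incompatible ways, and the hypothesis and aim on the start of oral feeding have no outcome

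*Combined protocol and SAP*

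**What the plan says.** All places are in the combined protocol and SAP.

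- **Aims (end of the introduction).** The second aim is to "determine the effect of sensory-motor stimulation offered by the mother on the onset of oral feeding".
- **Hypotheses (Material and methods).** The first of four is that infants stimulated by their mothers "Start taking oral feed at the same time as compared to the control group".
- **Schedule (Protocol).** The five-day intervention period has two parts: "Training phase (T): T1 and T2 (for mothers by the nurse") and then "Direct feeding phase (D): F1, 2, and 3 (oral feed was offered to neonate").
- **Mothers' arm (Experimental: Intervention group).** Before any D day there is "T1: Nurses performing all steps while mother observer status". On T2 nurses again carry out the steps and the mother gives the pacifier. Oral milk first appears at "D1: Mother performs all steps and oral milk was offered by the nurse while the mother observes".
- **Nurse arm (Control group / Sham Comparator).** "All steps were same as intervention group and was performed by trained staff nurses". No separate day-by-day schedule is given.
- **Outcomes (Primary Outcome Measure).** The definition, which applies to either arm, reads: "Transition time to full oral feeding is the time interval between commencement of perioral sensory stimulation on D1 to establishment of full oral feed". The adverse-outcome item in the same list identifies D1 with the first day of enrolment.
- **Table 3.** Time to full oral feed is 10 (7–13) days in the mothers' arm (n = 49) and 9 (7–13) in the nurse arm (n = 48), p = 0.531.

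**The concern.** The time origin fixes what the primary outcome can show. Here the sentence defining it calls D1 the start of stimulation, while the schedule has nurses stimulating on two earlier days in the mothers' arm. If the schedule is right, the interval runs from the first oral feed, and whatever happens before that feed lies outside it.

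This matters for the comparison being made. Mothers have to be trained and the nurses are already trained, so a later start of oral feeding is a plausible cost specific to delivery by mothers. A clock starting at the first oral feed cannot register such a cost. If only the mothers' arm had T1 and T2, its infants would also have received nurse-delivered stimulation before their clock started.

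The second matter is separate. The document sets out to learn whether oral feeding starts at the same time in both arms. That question needs an outcome of its own, wherever the primary clock begins.

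**Working it through.** **Step 1. The descriptions of D1 side by side.**

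| Place | What D1 is | Fits with T1 and T2 coming first? |
|---|---|---|
| Primary Outcome Measure, transition time | Start of stimulation | No: nurses perform all steps on T1 and T2 |
| Adverse-outcome item, same list | First day of enrolment | No: T1 and T2 are already study days |
| Protocol; Experimental group | First direct-feeding day | Yes |

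The first two could coincide with each other, but only if no stimulation precedes D1. Table 3 reports oral volumes on D1 (median 2.0 in each arm). That fits the third description without excluding the others. The 14-day limit inherits the problem. It is expressed in days of stimulation, while the recording days are labelled up to D14. If T1 is stimulation day 1, stimulation day 14 is D12 (14 − 2).

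**Step 2. How much time could be left out.** Let L be the number of stimulation days before D1. Adding a constant to every infant in an arm moves that arm's median by the same constant, so, counted from first stimulation, the difference in medians is

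(10 + L_mothers) − (9 + L_nurses) = 1 + (L_mothers − L_nurses).

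Stimulation is twice daily, so two lead-in days hold up to 2 × 2 = 4 sessions.

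| Reading | L, mothers / nurses | Medians from first stimulation | Difference | Sessions before the clock, mothers / nurses |
|---|---|---|---|---|
| Stimulation really starts on D1 | 0 / 0 | 10 vs 9 | 1 day | 0 / 0 |
| Both arms had T1 and T2 | 2 / 2 | 12 vs 11 | 1 day | up to 4 / up to 4 |
| Only the mothers' arm had T1 and T2 | 2 / 0 | 12 vs 9 | 3 days | up to 4 / 0 |

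Only the third reading changes the comparison.

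**Step 3. Hypotheses against listed outcomes.**

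| Hypothesis | Listed outcome that addresses it |
|---|---|
| 1. Same start of oral feeding | None |
| 2. Same amount at the start | Total volume, volume in first 5 minutes, overall transfer |
| 3. Same efficiency | Level 4 achievement, rate of transfer, proficiency |
| 4. No more adverse effects | Adverse events |

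The remaining outcomes are transition time and suck-swallow-breathe coordination. Transition time has D1 as its zero. On the Protocol schedule D1 is the first oral-feed day, so time to first feed on that clock is zero for every infant. The nearest recorded items are in Table 2: chronological age at enrolment, 13 (6–14) versus 9 (7–16) days, p = 0.925, and postmenstrual age at enrolment, 32 (31–33) weeks in both arms, p = 0.787. Both are listed as characteristics at enrolment and are tied to enrolment, not to the first oral feed.

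**The case against.** **A common lead-in is a fair reading.** The five-day period is set out before the two groups are named, the control steps are said to be the same, and the outcome is defined identically for both groups. Nothing says that controls skipped T1 and T2 or that feeding was delayed in the mothers' arm. This stands: a reader might infer a hidden training delay, but the documents do not show one. They do not exclude one either. T1 and T2 are described as training for mothers, and the control wording may refer only to the stimulation steps.

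**D1 may be enrolment.** Then nothing after enrolment is uncounted. That would remove the omitted time, but not the contradiction with the schedule. If enrolment were also the first oral-feed day, time from enrolment to first feed would be zero by construction, and hypothesis 1 could be addressed only through age at that day.

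**Hypothesis 1 may be loose wording for transition time.** The other three hypotheses match listed outcomes, so this is possible. Aim 2 names onset explicitly, which counts against it.

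**A significant difference could be computed.** A reader might add 2 days to the mothers' arm and conclude that the null result reverses. Assume SD = (13 − 7)/1.349 = 4.45. Then SE = 4.45 × √(1/49 + 1/48) = 0.90, and p = 0.531 gives z = 0.626, or 0.57 day. Adding 2 gives 2.57 days, z = 2.84, p about 0.005. This is illustration only. It assumes the lead-in in one arm, assumes the direction of a difference whose p-value carries no sign, and applies a normal approximation to data the document calls asymmetric. With the opposite sign, 2 − 0.57 = 1.43 days, z = 1.59, p about 0.11. The documents do not support a claim of reversal.

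**Replacing the primary outcome now would be post hoc.** Results are already reported in the same document. This stands and limits the fix.

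**Conclusion.** Two defects hold on the text alone. First, D1 has three descriptions that cannot all be true if T1 and T2 precede it, so the origin of the primary outcome is not defined. Second, hypothesis 1 and aim 2 have no outcome, so the trial cannot support a conclusion on whether oral feeding starts at the same time.

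A reader might take the second defect to follow from the first. It does not: hypothesis 1 is untested because no onset outcome is listed, and the D1 origin only compounds this.

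The effect on the reported comparison is conditional. It is nil if both arms had the same lead-in. If only the mothers' arm had T1 and T2, it is up to 2 uncounted days against a reported median difference of 1 day, making 3 days from first stimulation. This rests on the Protocol schedule having been followed and on a full two-day lead-in. Which reading is true has to come from the investigators.

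**What to change.** 1. Reconcile the passages on D1, define D1 once, and use that definition for transition time, adverse events and the 14-day limit.
2. State, by arm, how many days of stimulation preceded D1.
3. Add time from randomisation to first oral feed, by arm, as the outcome for hypothesis 1 and aim 2. If randomisation dates cannot be recovered, use time from enrolment, or postmenstrual or chronological age at first oral feed.
4. Keep D1 to full oral feed as the reported primary outcome, described by its true origin.
5. Add time from randomisation or enrolment to full oral feed as a supplementary analysis labelled post hoc, with the first stimulation day as the fallback origin.
6. State how randomised infants who never reached D1 are handled. Results give 130 randomised, 107 stimulated and 97 completing, so 130 − 107 = 23 had no stimulation and a further 107 − 97 = 10 did not complete. A D1 clock cannot start for an infant without a D1.
7. If the onset of oral feeding cannot be recovered, draw no conclusion on hypothesis 1 and withdraw any that has been drawn.

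The cost is retrieving dates from charts. The document lists ages and durations, and does not show that randomisation, first-stimulation and first-feed dates are on file. No new patients are needed. The result may be less favourable to the mothers' arm.

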 - Volume taken during the first 5 min (TV₅) out of total feed taken orally
 - Rate of transfer (RT) ml/min i.e., how long it neonate takes to finish oral feed.
 - Overall transfer (OT percent) volume taken/total volume prescribed. It shows trend towards oral feed establishment.
 - Proficiency (PRO percent) volume taken during the first 5 min/total volume prescribed.
 - SSB (Suck Swallow Breaths) coordination coordinated, developed pattern of suck swallow and breathe. It is a subjective assessment.

Statistical analysis

The statistical software IBM SPSS Statistics version 21 (SPSS, Chicago, IL) was used for the statistical analysis of the data. Appropriate bivariate analysis was performed to identify the unadjusted differences between the cases and controls. Categorical variables were expressed as frequencies and percentages. According to Shapiro Wilk test all continuous variables were asymmetrically distributed. Mann–Whitney U test was used for nonparametric continuous variables and were described as medians and inter quartile range (IQR). Fisher exact/Chi square test was used to compare categorical variables. Mann-Whitney test was used to compare continuous variables. The p-value of < 0.05 was taken as statistically significant.

Results

During the research period, 1009 newborns were admitted to the Neonatal Intensive Care Unit (NICU). Among them, 142 were born prematurely, with gestational ages falling between 28 and 34 weeks. Out of the preterm neonates, a total of 130 were eligible for the study, as 12 had to be excluded for various reasons. These exclusions included 2 cases where mothers experienced serious postnatal complications, 1 instance of parental refusal to participate, 1 case with incomplete data, and 8 cases that did not meet the inclusion criteria due to different reasons such as syndromic features, cleft lip and palate, suspected inborn error of metabolism (IEM), intraventricular hemorrhage (grade IV), and hemodynamically significant patent ductus arteriosus (HsPDA). Consequently, 130 neonates were included in the study and randomly assigned, with 65 in each group for intervention and control. Sensory motor stimulation (SMS) was administered to 107 of these neonates, and the study was completed with 97 neonates (as illustrated in Figure 1).

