Seizures ^a	7 (58.3%)	5 (41.7%)	0.394		
M A T E R N A L	Age ^b	29 (26 - 32)	30 (26.5 – 33)	0.138	
	Gravidity ^a	Primigravida	20 (43.5%)	26 (56.5%)	0.350
		2-3	22 (59.5%)	15 (40.5%)	
		≥ 4	7 (50.0%)	7 (50.0%)	
	Education ^a	Uneducated	2 (50.0%)	2 (50.0%)	0.699
		Primary	11 (52.4%)	10 (47.6)	
		Secondary	15 (42.9%)	20 (57.1%)	
		Higher	21 (56.8%)	16 (43.2%)	
	Previous preterm (yes) ^a	42 (52.5%)	38 (47.5%)	0.281	
	Job status (Housewife) ^a	29 (48.3%)	31 (51.7%)	0.368	
Hypertensive disorder ^a	29 (47.5%)	32 (52.5%)	0.290		
DM ^a	17 (50.0%)	17 (50.0%)	0.555		
Anemia ^a	25 (54.3%)	21 (45.7%)	0.304		

Table 2 : Feeding characteristics

Feeding characteristics	Experimental group (n=49)	Control group (n = 48)	p-value
PMA at enrollment (week)	32 (31 – 33)	32 (31 – 33)	0.787
ChA at enrollment (days)	13 (6 – 14)	9 (7 – 16)	0.925
Time to full gavage feed (days)	7 (5.5 – 13.5)	7 (6 – 14)	0.726
Discharge weight (kg)	1.48 (1.42 – 1.66)	1.48 (1.43 – 1.75)	0.698
Weight at enrollment (kg)	1.35 (1.25 – 1.54)	1.35 (1.21 – 1.60)	0.610
Duration of stay in NICU (days)	21 (15 – 29.5)	30 (16 – 30.75)	0.848
Milk Feed (ml/kg/day)			
Milk feed D1	120 (120 – 120)	120 (120 – 120)	0.302
Milk feed D2	120 (120 – 140)	120 (120 – 140)	0.871
Milk feed D3	140 (140 – 140)	140 (140 – 157.50)	0.109
Milk feed D5	150 (150 – 160)	160 (150 – 160)	0.361
Milk feed D7	160 (160 – 160)	160 (160 – 160)	0.184
Milk feed D14	160 (160 – 180)	160 (160 – 180)	0.758
Volume of feed prescribed (ml/feed)			
Volume prescribed D1	14 (12 – 15.5)	14 (12 – 16)	0.670
Volume prescribed D2	14 (12 – 17.5)	12.5 (12.25 – 19)	0.825
Volume prescribed D3	16 (14 – 17.5)	14 (14 – 20)	0.569
Volume prescribed D5	17 (15 – 19)	17 (15 – 21)	0.758
Volume prescribed D7	18 (16 – 20.5)	18 (16 – 22)	0.614
Volume prescribed D14	18 (16 – 22)	18 (16 – 24)	0.933

Table 3 : Study outcome

Outcome		Experimental gp (n=49)	Control gp (n=48)	p-value
Time to full oral feed (days)		10 (7 – 13)	9 (7 – 13)	0.531
Adverse events	D1	36 (53.7%)	31 (46.3%)	0.234
	D2	14 (50.0%)	14 (50.0%)	0.563
	D3	12 (50.0%)	12 (50.0%)	0.570
	D5	2 (100%)	0 (00%)	0.253
	D7 & 14	0 (00%)	0 (00%)	NA
L4 Efficacy on	D 1 -3	0 (00%)	0 (00%)	NA
	D5	12 (57.1%)	9 (42.9%)	0.331
	D7	16 (51.6%)	15 (48.4%)	0.528
	D14	35 (49.3%)	36 (50.7%)	0.434
Volume Taken Each feed	D1	2.0 (2.0 -7.0)	2.0 (2.0 -7.0)	0.803
	D2	5.0 (2.0 - 9.0)	3.0 (2.0 – 7.0)	0.558
	D3	7.0 (3.0 – 11)	4.0 (3.0 – 10.0)	0.540
	D5	8.0 (5.0 – 15)	6.5 (5.0 – 15)	0.521
	D7	9.0 (7.0 – 18)	7.5 (7.0 – 20)	0.951

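### The primary endpoint, transition time, has no stated value, rank or censoring rule for infants not on full oral feeds by day 14, and the follow-up window is contradictory

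*Combined protocol and SAP*

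**What the plan says.** Under Data Collection, transition time is the first primary outcome. The definition is: "Transition time to full oral feeding was the day at which baby was able to take oral feed of volume of 120-140ml/kg/day". Of its assessment the text says: "It was done daily till 14th day of perioral sensory motor stimulation".

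Three other statements describe a different or softer window:

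- Data Collection, on outcomes in general: these "measured were documented daily twice a day (11.00 and 17.00 hrs) until achievement of full oral feed".
- Procedure of intervention, on stimulation: it continued "till full oral feed establishment (expected time 28 days chronological age".
- Data Collection, on adverse outcome monitoring: it ran "till establishment of full oral feed (by D14 expected".

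Under Statistical analysis, "Mann-Whitney test was used to compare continuous variables", with medians and interquartile ranges as the summaries, and "The p-value of < 0.05 was taken as statistically significant". No time-to-event method is named.

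The Table 3 row "Time to full oral feed (days" gives a median of 10 (quartiles 7 and 13) in the experimental group and 9 (7 and 13) in the control group, p = 0.531. The column headings are n = 49 and n = 48. The number of infants not on full oral feeds at D14 is not reported.

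**The concern.** An infant who has not reached the target intake when reading stops has no transition time under the definition given. The plan calls attainment by D14 an expectation, so it foresees such infants, but it does not say how they enter the comparison. They could be left out, given day 14, given a later rank, or followed to an observed later day. These choices are not equivalent.

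The direction of the possible error matters here. The study hypothesis is that infants stimulated by mothers start oral feeding at the same time as those stimulated by nurses, and the Results conclude comparability from non-significant differences. Leaving out the slowest infants in each arm removes the part of the distribution where a delay would show most, so it biases towards the conclusion drawn.

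**Working it through.** The reported p = 0.531 cannot be reproduced without individual times. What can be checked is whether the text fixes a value for every infant, how many infants could be affected, and how much the handling could matter.

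**1. Is every infant given a value?** The definition supplies a day only if the intake is reached. The assessment sentence stops at day 14. The analysis section names a test but no rule for an infant without a day. Read literally, only attainers have a value.

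**2. Do the windows agree?** One sentence stops at day 14 of stimulation, one records until full oral feeding with no limit, and one expects full feeding at 28 days of age. The last can be set against age at enrolment in Table 2:

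| Group | Age at enrolment, median (quartiles) | 28 minus age |
|---|---|---|
| Experimental | 13 (6, 14) | 15 (14 to 22) |
| Control | 9 (7, 16) | 19 (12 to 21) |

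If D1 falls after two training days, each figure is 2 lower, giving medians of 13 and 17. Either way, for part of each arm the 28-day expectation lies past D14. The statements do not describe one window.

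**3. How many infants could lie beyond D14?** Assume Table 3 covers all 97 infants and uses the usual SPSS quartile position, 0.75 × (n + 1).

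- Experimental: 0.75 × 50 = 37.5, between the 37th and 38th ordered values. At most the 38th to 49th can exceed 14, which is 12 infants. For example, values of 11 and 15 average to 13.
- Control: 0.75 × 49 = 36.75, between the 36th and 37th. The outer limit is the 37th to 48th, again 12. (With whole days it is 11: a 37th value of 15 would need a 36th value of 7, since 7 + 0.75 × 8 = 13, and 7 is below the reported median of 9.)
- The minimum is 0 in each arm, since every value above 13 could be 14.

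The range is therefore 0 to 12 per arm. If non-attainers were left out of the table, the quartiles describe attainers only and this limit lapses.

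**4. How much could the handling matter?** This is an illustration, not an estimate. Assumptions: gamma times with shape 5 and scale 2.0 in the control group, rounded up to whole days (quartiles 7, 10 and 13); scale 2.6 in the maternal group, a 30% slowing; 48 and 49 infants; two-sided 0.05.

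- Mean before rounding: 5 × 2.0 = 10 days against 5 × 2.6 = 13 days, a true difference of 3.0 days.
- Not reached by D14: about 17% of controls and 38% of the maternal group.
- Mean difference among those who finish by D14: about 0.9 days.

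| Assumed control times | All times known | Non-attainers left out | Non-attainers tied later than 14 |
|---|---|---|---|
| Gamma, shape 5, scale 2.0 | about 0.78 | about 0.26 | about 0.75 |
| Gamma, shape 4, scale 2.6 | about 0.67 | about 0.17 | about 0.63 |
| Log-normal, median 9.5 | 0.78 | 0.35 | 0.76 |

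Entries are Mann-Whitney power for a 1.3-fold longer time. With no true difference, the log-normal setting gives type I error of 4.8% with complete times and 4.7% with the tied late rank.

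**5. Can the choice decide a single result?** Take constructed samples with near-identical times among attainers. With 12 against 6 non-attainers, p = 0.30 when they are ranked last and 0.99 when they are left out. With 12 against 0, the values are 0.04 and 0.99. These samples do not match Table 3 (with no non-attainers the control upper quartile is 11, not 13); they show only that the rule matters.

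**The case against.** **The test itself is sound.** A reader might infer that Mann-Whitney is invalid unless every infant has a finished time. It is not: with one common cut-off, all non-attainers can be tied as latest, and the test keeps its error rate and nearly all its power. The gap is the missing rule, not the test.

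**Later times may exist.** Recording and stimulation are elsewhere said to run to full oral feeding, so every infant may have an observed day. This is possible, but the sentence specific to the primary endpoint stops at day 14. The contradiction stands until the sponsor resolves it.

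**No analysed infant is shown to lack a time.** This stands. The Table 3 row carries no reduced n, and an upper quartile of 13 lies inside the window.

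**The overall-transfer figures do not show failure.** A reader might multiply the D14 lower quartile of overall transfer in the experimental group by the median prescription, 0.87 × 160 = 139 ml/kg/day, and infer that a quarter of that arm had failed. But 139 lies inside the 120-140 range, and the lower end needs only 120 / 160 = 75%. The control figure gives 0.879 × 160 = 140.6. The product also joins separate summaries of two variables, and the outcome was tabulated at a single 11.00 feed.

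**The simulated loss does not fit the table well.** Under the gamma settings, leaving out times beyond D14 gives control quartiles of about 6 to 7, 9 and 11, and an upper quartile of 13 or more in only about 2 to 5% of samples; Table 3 reports 13. The first setting also expects about 0.38 × 49 = 19 maternal-group infants beyond D14, more than the 12 that a table of all 97 allows. This argues against reading the loss as what happened. It does not settle the matter, because the gamma times were matched to Table 3 as if it covered everyone; if it covers attainers only, the true times run longer than assumed.

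**Conclusion.** The concern holds as a gap in the primary analysis. Its two parts rest on the text alone: no rule covers an infant not on full oral feeds at D14, and the statements about follow-up conflict.

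The consequence is conditional. If non-attainers were left out, the comparison is biased towards sameness, and the loss of power could be large under the assumptions shown. If they were ranked last, or if later days were observed and used, the comparison is essentially sound. If Table 3 already includes every infant in one of these ways, the reported medians stand.

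The documents do not support saying that infants were dropped, that a known number failed, or that the reported result is wrong. Because this is a primary endpoint behind a claim of comparability, the point should be settled before that claim is relied on.

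**What to change.** 1. Reconcile the sentences on the window under Data Collection and Procedure of intervention, and state when reading of the primary endpoint ended.
2. Report, by arm, how many analysed infants had not reached full oral feeding by D14.
3. Include every analysed infant under one stated rule:
   - censor at D14, with Kaplan-Meier curves, a log-rank test, and the difference in restricted mean time to D14 with a 95% interval; or
   - keep Mann-Whitney with all non-attainers tied at one rank later than 14.
4. If later times were observed for all infants, say so and use them.

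The tied rank is the smaller change. The censored analysis adds an interval for the difference, which serves a claim of comparability better than a p-value, and it can also handle infants whose observation ended before D14.

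The cost is a few sentences and one re-analysis of data already held, with no new data collection. If follow-up did run to full oral feeding for everyone, one sentence and the counts settle the point.
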